3.1. Duration of Study

Phase 1: Participants will be asked to complete a one-time interview lasting approximately 60 minutes.

Phase 2: Participants will be asked to complete the intervention over a period of 6 weeks. Participants will be asked to complete 6-week online self-management educational modules and 6 weekly peer mentor calls to facilitate engagement with the online modules and offer specialized support.

3.2 Study Sites

Phase 1: Interviews will be conducted at the Rutgers Cancer Institute of New Jersey or via phone.

Phase 2: Peer mentors will be trained at the Rutgers Cancer Institute of New Jersey or via phone or online webinars. Participants will receive intervention materials online, via email, or via text messaging.

3.3 Sample Size Justification

Phase 1: Total sample size is 24-28, including 10 AYA survivors, 10 parents of AYA survivors, and 4-8 physicians who work with AYA survivors. Qualitative data will be analyzed on a continuing basis. Pooling data across participants, we expect 24-28 interviews will be adequate to achieve data saturation (that is, no new themes emerge from additional participants).

Phase 2: 40 AYA survivors and 20 peer mentors will be recruited for the pilot trial to evaluate feasibility (primary objective) and preliminary outcomes (secondary objective). As this is a feasibility study, we recognize we are underpowered to detect small or medium

Promoting Follow-Up Care Self-Management for Adolescent and Young Adult (AYA) Childhood Cancer Survivors

[name], MPH

effects. Published data suggest 5-9% of survivors are African American or Hispanic;²² data from the NJSCR show greater diversity, with 11.6% of patients diagnosed with cancer at age 10-19 during the period of 2008-2012 reporting as African American, 19% reporting as Hispanic, and 5.7% as Asian American/Pacific Islander. We will oversample these groups.

3.4 Subject Selection and Enrollment Considerations

3.5.1 Inclusion Criteria

Phase 1:

Patient eligibility includes:

- (1) age 18-25
- (2) at least 1.5 years from treatment (which is a typical time for preparation to transfer to long-term follow-up care)

Parent eligibility includes:

- (1) caregiver of a pediatric cancer survivor age 18-25 who was primary caregiver at diagnosis
- (2) patient is at least 1.5 years from treatment

Provider eligibility:

- (1) health professional who works with childhood cancer survivors ages 18 to 25

Phase 2:

Peer mentor eligibility includes:

- (1) age 21-29
- (2) at least 1.5 years from treatment
- (3) self-reported primary responsibility for care and “complete readiness” using the Readiness for Transition Questionnaire²³

Patient eligibility includes:

- (1) age 18-25
- (2) at least 1.5 years from treatment
- (3) currently does not independently self-manage follow-up care according to self-report (i.e., reports low readiness to assume total responsibility for care [score of 1 or 2 out of 4 on overall readiness item OR scores <3 on any of the 10-item responsibility scale) using the Readiness for Transition Questionnaire²³)

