1.1 Objectives/Hypotheses

Promoting Follow-Up Care Self-Management for Adolescent and Young Adult (AYA) Childhood Cancer Survivors

[name], MPH

Aim 1: Adapt PSST with peer mentoring to improve AYA self-management of long-term follow-up care.

Qualitative research with AYA cancer survivors, parents, and healthcare providers will be conducted to adapt an evidence-based problem-solving skills training (PSST) program to address the needs of AYA survivors.

Aim 2: Evaluate the feasibility of the self-management + peer mentoring program in a pilot RCT.

We will examine feasibility through study enrollment rates, retention rates, adherence to the intervention, reasons for study drop out, and patient and mentor satisfaction with the program.

Hypothesis 1: Based on literature, we expect enrollment >50% of eligible patients and retention >75%.

Hypothesis 2: We expect patients enrolled in the mentor program to complete >75% of intervention sessions

Aim 3: Assess preliminary outcomes of the peer mentoring program.

Hypothesis 3: Participants in the mentor group will demonstrate improvement in self-management skills, transition readiness, and anxiety.

2. Background and Significance

The transition to adult self-management of health care is often ineffectively managed by AYAs.

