4.2 Dependent Variables or Outcome Measures

Phase 1: The primary outcome measure is qualitative interview data. Interviews will be transcribed for analysis (see Data Handling and Statistical Analysis section for details). Participants will also be asked to complete the questionnaires selected for Phase 2 and provide feedback to the study staff regarding how well the questionnaires capture self-management of survivorship care.

Phase 2: The following standardized measures will be administered at baseline and immediately post-intervention (~6 weeks), except where noted:

Transition readiness. The Readiness for Transition Questionnaire – Survivor Version (RTQ)²³ is a 22-item scale evaluating transition readiness for cancer survivors. Respondents are asked to rate the degree to which they are responsible for various aspects of their health care, such as knowing their survivorship care plan, scheduling visits, and filling prescriptions. They are separately asked to rate the degree to which their parents are responsible for managing the same aspects of their care. Two questions ask about the survivors' overall perception of their readiness to transfer to an adult-approach to health care. The RTQ has demonstrated adequate reliability.²³

The Transition Readiness Inventory (TRI), developed using the SMART framework,²⁸ is a comprehensive measure of multiple components of transition readiness. While the RTQ focuses on responsibility for behaviors, the TRI focuses on behaviors *and knowledge, attitudes, and beliefs*. Specifically, the TRI yields a total score and provides scales for the following targets of our intervention: knowledge, self-management skills, self-efficacy for managing care, goals/motivation, and communication with family and providers around survivorship care. The TRI has shown adequate reliability and content validity,^{28,29} and evidence of predictive validity of engagement in adult healthcare.²⁹ We will utilize the total TRI score.

Anxiety. PROMIS Depression and PROMIS Anxiety measures are validated 8-item measures of depressive symptoms and anxiety. We will examine cancer-related anxiety using the Fear of Recurrence Scale,³⁰ which has been used with young adult survivors of childhood cancers.³¹ Finally, we will adapt items to examine anxiety related to healthcare transition and cancer late effects. We will also use the Cancer Related Worry Scale to assess participants' concerns related to their cancer past and future.

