To assess the preliminary outcomes of the peer mentor self-management program, we will evaluate whether participants in the program demonstrate improvement in transition readiness and the impact of cancer, and reductions in symptoms of depression and anxiety. We will also explore adherence outcomes. We will compare scores on outcome measures at the end of 6-week assessment using dependent/paired t-tests. Since the primary purpose of this project is to evaluate feasibility, we recognize that we do not have adequate power to detect small to medium statistical effects. Exit interviews will be reviewed to identify strengths of the intervention, weaknesses of the intervention, and ideas to improve the intervention.

6. Data and Safety Monitoring

This study is minimal risk. The PI and co-investigators will monitor for adverse events and report any events according to RBHS IRB guidelines.

7. Reporting Results

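### The RTQ both selects low scorers and serves as a pre-post outcome; unless the analysed baseline is separate from the screening score, regression to the mean can mimic improvement on it

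*Combined protocol and SAP*

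**What the plan says.** - **Selection.** Section 3.5.1 (Phase 2, patient criterion 3) admits survivors who do not yet manage their own care, defined on the RTQ as a "score of 1 or 2 out of 4 on overall readiness item OR scores <3 on any of the 10-item responsibility scale".
- **Outcome.** Section 4.2 lists the same questionnaire first among the Phase 2 outcomes; it "is a 22-item scale evaluating transition readiness for cancer survivors". On timing: "The following standardized measures will be administered at baseline and immediately post-intervention (~6 weeks), except where noted". No exception is noted for the RTQ. The Transition Readiness Inventory (TRI) total is a second readiness measure and plays no part in eligibility.
- **Hypothesis.** Hypothesis 3 in Section 1.1 reads: "Participants in the mentor group will demonstrate improvement in self-management skills, transition readiness, and anxiety". It names no comparator.
- **Analysis.** Section 5: "we will evaluate whether participants in the program demonstrate improvement in transition readiness", and "We will compare scores on outcome measures at the end of 6-week assessment using dependent/paired t-tests". No between-arm test is given.
- **Design label.** Aim 2 is to "Evaluate the feasibility of the self-management + peer mentoring program in a pilot RCT", and Section 3.5.3 also calls the trial randomized. No control condition or allocation ratio is described.
- **Silent point.** Nothing says whether the RTQ answers that establish eligibility are also the baseline RTQ that is analysed.

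**The concern.** When people are chosen because a score is low, part of that low score is measurement error in the unfavourable direction. On the next administration the error is redrawn and the group mean rises, even if nobody has changed. A paired test that uses the selecting score as its starting point counts this rise as improvement. A within-person test has no means of separating it from benefit. A concurrent randomized arm would show the same rise, so a comparison between arms would remove it, but Section 5 plans none.

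At stake is the reading of the RTQ part of Hypothesis 3. A favourable paired result could be reported as improved readiness when some or all of it comes from the way patients were selected.

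**Working it through.** **Inputs**
- Selection rule: Section 3.5.1. Outcome and timing: Section 4.2. Test: Section 5.
- Significance level and sidedness are not stated. Assumed two-sided 0.05, so 0.05/2 = 2.5% in the favourable direction.
- Sample size is 40 survivors (Section 3.3), with no allocation ratio. The paired n is 40 if all receive the program, or 40/2 = 20 under an assumed 1:1 split. At the 75% retention threshold of Section 1.1, 40 becomes 0.75 × 40 = 30.
- RTQ reliability: Section 4.2 calls it adequate and gives no figure. The share of survivors who qualify is not given. Which RTQ score is analysed is not stated; the 10-item responsibility mean is assumed.
- No power calculation lies behind the 40, so there is no figure of the plan's own to reproduce.

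**Step 1: direction of the bias.** Take a single normal score with reliability r, selection below a cut c, no true effect, and the screening score used as the starting value. Then

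expected gain = (1 − r) × φ(c)/Φ(c), in SD units.

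With r = 0.7 and the lower half selected (c = 0), this is 0.3 × 0.399/0.5 = 0.24 SD. With 80% selected it is 0.3 × 0.280/0.8 = 0.105 SD. If a separate baseline is taken and its error correlates ρ with the screening error, the gain is ρ times that value: for an assumed ρ = 0.5, 0.5 × 0.24 = 0.12 SD; for ρ = 0, none. This shows sign and mechanism only, because the plan does not select on a total score.

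**Step 2: the plan's rule.** Simulate one overall item and ten responsibility items, each scored 1–4. A subject is eligible if the overall item is 1 or 2, or if any of the ten is below 3. There is no true effect, and the screening 10-item mean is reused as baseline. Assumed: item correlation 0.3–0.5, item reliability 0.6–0.8, independent item errors. The table gives the frequency of a significant false improvement (nominal 2.5%).

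| Chance that an item is below 3 | Share qualifying | n=20 | n=40 |
|---|---|---|---|
| 10% | 42–52% | about 8–12% | about 14–21% |
| 20–50% | 63–97% | about 3–10% (range over both sizes) | as left |

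In the first row the spurious gain is about 0.07–0.13 SD. The ends of the ranges shift slightly with where the remaining item cut points are put. Error shared across items on one occasion would raise them.

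A second item-level simulation, with item reliability 0.6 and its own assumed item distributions, gave at n=40: 3% when 96% qualify, 12% when 63% do, 28% when 37% do and 59% when 17% do. The result is therefore driven mainly by how narrow the selection is.

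**Step 3: what removes it.** With a fresh baseline whose error is independent of screening, false improvement is about 2–3%. Comparing RTQ change between arms, 20 against 20, rejects in 4.4–5.3% of trials against 5% two-sided, even with the screening score as baseline. The price is precision: with 20 per arm, the normal approximation gives 35% power at a standardized difference of 0.5 and 72% at 0.8.

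**The case against.** The best defence is that the documents lean towards a separate baseline. Section 3.5.4 sends the consent link to people already found eligible, so eligibility is settled before consent. Section 4.2 has the measures given at baseline and notes no exception for the RTQ. Section 3.5.5 pays for two assessments. Read together, these suggest a telephone screen followed by a post-consent battery, and then the bias largely goes. This stands as the more natural reading. It is not a statement, however: carrying screening answers forward is not excluded, and a baseline taken soon after screening may share some of its error.

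Four stronger readings are tempting and not supported:
- A reader might infer that the RTQ result is certainly biased. The documents do not say that the screening score is reused.
- A reader might take the 0.24 SD of Step 1 as the size. That figure comes from keeping the lowest half on one total score. The plan's rule is one overall item or any one of ten, which truncates the scale mean much less.
- A reader might infer that Hypothesis 3 as a whole is undermined. The TRI and the anxiety measures are not used for selection, so this mechanism does not act on them directly.
- A reader might infer that a false signal would decide a later trial. No follow-on trial or progression rule based on the RTQ is described, and the stated thresholds concern enrollment, retention and session completion.

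It can also be said that the missing comparator is a larger, separate matter. That is fair: once arms are compared, this problem nearly disappears. The baseline still needs one clarifying sentence.

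**Conclusion.** The point holds in a limited form. The RTQ is both selector and outcome, the only specified test is within-person, and the origin of the baseline score is left open. If the screening score is reused, chance improvement on the RTQ exceeds its nominal 2.5%: slightly when most survivors qualify, and several-fold when about half or fewer do. If the baseline is fresh with independent error, the rate is essentially nominal.

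The size cannot be fixed from the documents. The figures rest on assumed item reliability, item correlation and qualifying share, on the 10-item mean as the analysed score, and on a two-sided 0.05 level. The n=40 figures further need all 40 in the program with no dropout. The outcome is secondary and preliminary; the feasibility objective is not affected. It should be corrected because the wording is cheap to change now, while a reused baseline cannot be repaired after enrolment.

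**What to change.** 1. In Section 5, base any statement of RTQ benefit on the between-arm difference at 6 weeks adjusted for baseline RTQ, and keep the paired change as description only. This requires the comparator implied by the randomized label to be described, with the allocation ratio.
2. In Sections 3.5.1 and 4.2, state that the screening RTQ decides eligibility only and that the analysed baseline RTQ is a new administration after consent.
3. If there is no comparator, do not read RTQ pre-post change alone as improvement. Report it beside the TRI total, which is not used for selection.

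Cost: wording, at most one repeat of a 22-item scale per participant, a less precise between-arm estimate (see the power figures in Step 3), and possibly a less favourable RTQ result.

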3.5.2 Exclusion Criteria

Phase 1:

Patient exclusion criteria includes:

- (1) physician- or self-reported cognitive delay or impairment that would prevent self-management of healthcare

Parent exclusion criteria includes:

- (1) patient has physician- or caregiver-reported cognitive delay or impairment that would prevent self-management of healthcare

Promoting Follow-Up Care Self-Management for Adolescent and Young Adult (AYA) Childhood Cancer Survivors

[name], MPH

No provider exclusion criteria

Phase 2:

Patient exclusion criteria includes:

- (1) physician- or self-reported cognitive delay or impairment that would prevent self-management of healthcare
- (2) patients with cancer diagnoses that are not typically considered pediatric cancer, including basal and squamous cell skin cancer, breast, colorectal, lung, melanoma, merkel cell skin cancer, ovarian, testicular, kidney cancer diagnosed at age >17, and nasopharyngeal diagnosed at age > 17.

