4.1 Independent Variables or Interventions

Phase 1: Semi-structured interview guides will be used to conduct interviews. The goal of the interviews is to understand patient, parent, and provider perspectives on the challenges faced by AYAs in managing their health care and on how PSST materials can be adapted to address the challenges of self-management of care.

Phase 2: Independent variables include demographics (age, gender, socioeconomic status, education, employment status, living at home or independently) and cancer diagnosis and treatment history (i.e., diagnosis, time since treatment completion, types of treatment received). Diagnosis and date of diagnosis will be obtained from NJSCR records and the remaining information from self-report.

Peer Mentoring Intervention. Based on initial interviews and feedback on the PSST intervention, we identified five major themes to be addressed in our program. The intervention will include two components: (1) online self-management educational modules using the Rutgers Canvas online course platform and (2) weekly video-conference calls on Doxy.me between the peer mentor and participant. Table 1 shows the content of the five online modules based on preliminary work. Participants are expected to complete one module per week in addition to a call with their mentors. Each module takes approximately 30 minutes to complete and ends with a personalized assignment for the participant to complete on his/her own (e.g., obtain survivorship care plan, make an appointment, practice communication skills).

Participants will be matched with a peer mentor of the same sex and cancer type to the extent possible.^{24,25} The objectives of the first mentor call are to build rapport, exchange stories regarding current long-term follow-up care, and identify the participant's self-management

Promoting Follow-Up Care Self-Management for Adolescent and Young Adult (AYA) Childhood Cancer Survivors

[name], MPH

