Participants will complete surveys online or via paper (depending on participants' choice). Paper surveys will be identified using only a subject number and will be entered into the database by study staff and kept in a locked filing cabinet accessible only by authorized study staff. We will keep a separate electronic key linking codes and subject names on the PI's department drive. This key will be destroyed at the end of the study. De-identified data will be kept indefinitely. Audio files of video/phone calls between peer mentors and mentees will be recorded using the peer mentor's handheld audio recorder. The peer mentor will then use Rutgers Large File Transfer Service (LiFT) to securely upload the files for the study team to review. This service allows both internal and external users to upload files securely with their email and password. The peer mentors will be instructed to destroy the files after they have successfully uploaded files to Rutgers LiFT for study team to review. Peer mentors will receive training on how to securely transfer the files and delete the files from their devices during the mandatory in-person peer mentor training. The study team will download the files via the secure LiFT service and store them on the Rutgers secure shared drive accessed via a password-protected computer. For participant exit interviews, study staff will record the interview, transfer to the secure shared drive (access limited to pertinent research team members). Recordings will be transcribed as soon as possible, removing any identifying information from the written document. Recordings will be destroyed upon completion of the study procedures.

Data Analysis: We will examine feasibility through study enrollment rates, retention rates, reasons for study drop out, adherence to the intervention, and patient and mentor satisfaction with the program. Descriptive analyses (frequencies, means) will be used to evaluate our hypotheses regarding expected enrollment (>50%), retention (>75%), and completion of intervention sessions (>75%). We based these predictions using the literature describing barriers

Promoting Follow-Up Care Self-Management for Adolescent and Young Adult (AYA) Childhood Cancer Survivors

[name], MPH

to recruiting AYA participants³⁹ and the team's collective experience in intervention development and implementation.

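### Does Phase 2 need a general age-at-diagnosis limit, or a planned summary of age at diagnosis, to describe childhood cancer survivors?

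*Combined protocol and SAP*

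**What the plan says.** Section 3.5.1 gives three Phase 2 patient criteria: age 18-25; item "2) at least 1.5 years from treatment"; and low self-reported readiness on the Readiness for Transition Questionnaire (RTQ). None concerns age at diagnosis.

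Section 3.5.2 excludes, for Phase 2, "patients with cancer diagnoses that are not typically considered pediatric cancer", and then names types. Most are excluded at any age. Only the last two carry an age: "kidney cancer diagnosed at age >17, and nasopharyngeal diagnosed at age > 17".

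Section 3.3 cites state registry figures on race and ethnicity for "patients diagnosed with cancer at age 10-19 during the period of 2008-2012". These support a plan to oversample and are not an eligibility limit. Section 3.5.3 recruits trial participants through that registry and adds no filter on age at diagnosis.

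Section 4.1 lists the cancer-history variables as "diagnosis, time since treatment completion, types of treatment received" and current age among the demographics. It then adds: "Diagnosis and date of diagnosis will be obtained from NJSCR records". Section 5 plans descriptive analyses of enrollment, retention and session completion, and paired t-tests on the outcome scores. It describes no baseline summary.

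**The concern.** The title and section 1 present the trial as one of childhood cancer survivors who are moving from parent-led to self-managed follow-up. Someone first treated as an adult may never have had parent-led cancer care, yet can meet the Phase 2 criteria. The protocol does not say whether this is intended. The only two ages at diagnosis it mentions (above 17 in section 3.5.2, and 10-19 in section 3.3) are not applied generally.

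What would be at stake is whom the results describe. Feasibility is the primary objective, and its rates will be read as applying to the title population. If later-onset participants were enrolled and the report did not show age at diagnosis, a reader could not tell how well that label fits.

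**Working it through.** The plan states no figure on this point to reproduce. The check is a reading of the criteria plus arithmetic on the age window.

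**How late can diagnosis be?** Inputs: age 18-25 (section 3.5.1), read as 18.0 to under 26.0; at least 1.5 years from treatment (section 3.5.1); treatment length T in years, which the documents do not give.

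- Latest age at diagnosis = 26.0 − 1.5 − T = 24.5 − T.
- T = 0 gives the upper bound, under 24.5. Assuming T = 1, 2 or 3 gives under 23.5, 22.5 or 21.5.
- Distance past the 18th birthday at T = 0: 24.5 − 18.0 = 6.5 years.
- Distance past the end of the 10-19 group (the 20th birthday) at T = 0: 24.5 − 20.0 = 4.5 years.
- If 25 is read as exactly 25.0, the bound is 25.0 − 1.5 = 23.5, which is 5.5 and 3.5 years past those two points.
- Earliest age at which someone diagnosed at 18 qualifies: 18.0 + 1.5 + T, that is 19.5 at T = 0.

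The wording therefore does admit diagnoses at 18 or later under each of these assumptions.

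**Is the intent really open?** In completed years, above 17 means 18 or older. If a general limit at that age applied, the qualifier on kidney and nasopharyngeal cancer would do no work, because every case diagnosed at 18 or older would already be out. The age is written out separately for each of the two types and not for the others. The reading that gives these words a purpose is eligibility by type, with age relevant for two types.

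**Does another section contradict that?** None gives an age that defines childhood cancer. The 10-19 registry group contains diagnoses at 18 and 19, so the protocol's own picture of its source population already passes 18.

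**Can age at diagnosis be obtained?** Age at diagnosis = age at enrollment − (enrollment date − date of diagnosis). Age and date of diagnosis are both in section 4.1. If age is held only in completed years, the result is known to within one year. No new data collection is needed.

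**Which planned result depends on it?** Enrollment is a proportion of eligible patients. With no general age limit written, age at diagnosis decides eligibility only for the two named types, so this point leaves the denominator countable. Retention, session completion and the paired comparisons do not use age at diagnosis.

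**The case for a change.** The best case for a change is that it costs almost nothing and that the written criteria carry more weight in Phase 2. Phase 1 draws its survivors from a long-term follow-up clinic, whereas Phase 2 draws on a state registry, whose staff must decide who is eligible from the protocol's words. The readiness criterion does not fully secure the target group either: a score below 3 on any one of ten responsibility items is enough, and that does not show that a parent ever managed the care. The RTQ does ask about parents ("They are separately asked to rate the degree to which their parents are responsible for managing the same aspects of their care"), but as an outcome measure, not as an entry criterion. Collecting a date of diagnosis also does not oblige anyone to report it.

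Part of this stands. Age at diagnosis would be a useful line in the baseline table, for example median, range, and number and percentage diagnosed at 18 or older. But section 5 specifies no baseline summary for any variable, so its silence on this one reflects the brevity of a pilot protocol. Registry staff can apply the criteria as written, because a limit that is not stated is not applied. Where judgment is needed, for unlisted types, it concerns cancer type and not age. The readiness criterion, though imperfect, selects people who report not yet managing their own follow-up, which is the state the program addresses.

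**Conclusion.** No change to the plan is needed. It is true that typically pediatric cancers diagnosed at 18 or later are eligible, up to an age just under 24.5 years less treatment time. That is neither an error nor a contradiction: it is the natural reading of a type-based rule, and it fits a trial whose title covers adolescents and young adults.

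The gap in the variable list is one that analysts fill as a matter of course from data already collected. Following the plan as written gives the same rates and the same comparisons. The 24.5-year bound assumes enrollment just before the 26th birthday and no treatment time. The documents give no count of such participants among the 40, so the practical size is unknown and may be nil. The conclusion rests on reading the above-17 qualifier as belonging to kidney and nasopharyngeal cancer only, which its placement supports.
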